1.1.2. RZL-012 Formulation Development

The active ingredient RZL-012 drug substance was manufactured by Pharmacore, High Point NC, USA. The drug product, 5 % RZL-012 in F12 liquid formulation (250 mg RZL/5 mL vial = 50 mg RZL/mL), was manufactured and packaged at Nextar Ltd, Ness-Ziona, Israel. RZL-012 in F12, which was once defined as RZL-012 F12, is now defined as RZL-012. The active ingredient and formulation manufacturing and packing were in accordance with clinical Good Manufacturing Practices (cGMPs).

1.2. CLINICAL STUDIES CONDUCTED BY RAZIEL

RZL-012 has been tested in 3 clinical trials, having a total of 54 exposed subjects at single doses of up to 180 mg/subject. Table 1 describes the clinical trials conducted by Raziel Therapeutics.

Study ID STATUS	Phase	Country	Study Title	Study Design	Dosing Regimen	Study Population
RZL-012-P0US- 001.3 COMPLETED	0	USA	Phase 0 Study for evaluation of safety and thermogenesis in Overweight Healthy Volunteers injected with 3 escalating Doses of RZL-012	A randomized, double-blind, vehicle-controlled, dose-escalation study with 8 subjects/cohort, (6 active and 2 controls)	Cohort 1: 5 mg Cohort 2: 10 mg Cohort 3: 20 mg	Healthy, 20-40 year old, overweight by Body Mass Index (BMI) definition ($25 < BMI \le 34.9$), adult males.
RZL-012-P2aUS- 001.4 COMPLETED	2A (obese)	USA	A Double Blind, Randomized, Placebo Controlled, Dose Escalation Phase 2a Clinical Trial for the Evaluation of Safety and Thermogenesis- induction of RZL-012 in Overweight and Obese Volunteers	A randomized, double-blind, placebo-controlled, consecutive 4 cohort, dose escalation clinical trial	Cohort 1: 40 mg Cohort 2: 80 mg Cohort 3: 120 mg Cohort 4: 180 mg	Adult male subjects 20– 60 years old, with 27.5 < BMI ≤ 34.9

Table 1: Summary of Clinical Trials Conducted by Raziel Therapeutics

Study ID STATUS	Phase	Country	Study Title	Study Design	Dosing Regimen	Study Population
RZL-012-FD- P2aUS-001 COMPLETED	2A (DD and lipede ma)	USA	An Open Label, Phase 2a Clinical Trial for the Evaluation of Safety and Efficacy of RZL- 012 for the Treatment of Women with Lipedema Involving Substantial Fat above the Knee or of Women and Men with Nodular Dercum's Disease	Open-label safety and efficacy clinical trial	Cohort 1 DD: up to 40 mg RZL- 012 per subject in 6 subjects Cohort 2 Lipedema: up to 80 mg RZL-012 per subject in 6 subjects	DD : men 20–65 years old and post- menopausal (at least 2 years) women <65 years old with nodular Dercum's disease Lipedema : post- menopausal (at least 2 years) women <65 years old with lipedema involving substantial fat above th knee

1.2.1. Overall Safety Summary:

The majority of adverse events (AE)s after RZL-012 injection were related to local injection site reactions. There was no correlation between RZL-012 dose increase and severity or duration of local reaction. Most injection site reactions were transient and were not observed for more than 28 days following injection. There were no significant changes in blood parameter values except for 2 cases as reported in the 2 studies indicated for obesity. In study RZL-012-P0US-01.3 (Phase 0) there was one subject injected with 20 mg of RZL-012 who demonstrated a significant increase in liver enzymes. However, when these parameters were reviewed carefully among other subjects injected with higher doses of RZL-012 (up to 9 times i.e., 180 mg), this phenomenon was not repeated. In preclinical studies which were conducted by Raziel, a rise in aspartate aminotransferase (AST) enzyme levels was observed at high doses in female rats (20 mg/rat equivalent to a human dose >>500 mg/subject), getting back to normal levels within 14 days following injection. The relationship between RZL-012 injection and increased levels of liver enzymes in this subject is not completely understood. Raziel Therapeutics continues to monitor closely for any changes in liver enzymes.

The second case was reported in RZL-012-P2aUS-01.4 study (Phase 2a in obese subjects). Subjects which were injected with the maximal dose of 180 mg had an average 3-fold increase of D-dimer values at Day 3 compared to Day -1. However, levels went down by Day 7.

1.2.2. Efficacy summary:

Measurements of lipoma size in 6 DD subjects who participated in study RZL-012-FD-P2aUS-001, included ultrasound measurements of height, width and length for 21 injected lipomas. Each subject was dosed up to 40mg of RZL-012 that was injected into several lipomas. The mean reduction in lipomas height on day 56 after injection vs. baseline was $47.9\pm44.1\%$ (P<0.001). Lipoma pain was measured by the comparative pain scale in 19 of 21 injected lipomas in 6 DD pts (specific pain assessment per each lipoma). The mean reduction in lipoma pain on day 56 after injection vs. baseline was $70.7\pm36.9\%$ (P<0.0001).

Further details are provided in the IB.

The current clinical trial in DD subjects will have a single injection session of RZL-012 at doses up to 240 mg/subject, (up to 48 injections) and will be the first trial to assess efficacy of RZL-012 vs. placebo in DD subjects.

2. PURPOSE AND STUDY OBJECTIVES

2.1. PURPOSE

This is a double blind, randomized, multi-center, placebo controlled 2b clinical trial for the evaluation of efficacy and safety of RZL-012 in women or men having DD lipomas.

2.2. STUDY OBJECTIVES

The primary and secondary endpoints described below relates to the placebo-controlled study.

2.2.1. Primary

To evaluate the average percent reduction in lipoma/nodule height on day 84 after injection vs baseline- evaluated by ultrasound in the RZL treatment group compared to the placebo group.

2.2.2. Secondary

The secondary objectives are to evaluate the efficacy and safety of RZL-012 subcutaneous injections in the lipomas vs. placebo by:

- Evaluating the reduction in local pain score per lipoma/nodule on Day 84 vs baseline as measured by the comparative pain scale. This secondary endpoint will be a key endpoint.
- Evaluating safety and tolerability of RZL-012 injection in DD subjects.
- Evaluating percent lipomas/nodules with height reduction of at least 75% on Day 84 vs baseline as measured by ultrasound.

2.2.3. Exploratory

- Improvement in Quality of Life – using a QOL questionnaire

2.3. DESCRIPTION OF STUDY DESIGN

This is a multi-center, randomized, double blind, placebo controlled clinical trial in DD subjects having lipomas. Subjects will be randomized, in a 1:1 ratio, into two groups injected with either RZL-012 or vehicle.

Once the study ends and codes are opened, 84 days after dosing, placebo-treated subjects will be offered the option of receiving treatment with RZL-012 and followed up for an additional 84 days.

At least 4 lipomas/nodules, preferably 6, and no more than 8, will be injected per subject. Dosing will be according to lipoma size, where the total injected dose will not exceed 240 mg per patient (48 injections at 5mg/injection).

2.4. DOSE RATIONALE

In all previous completed clinical trials, the maximal RZL-012 dose per injection site was 5 mg, and a distance of 1-3 cm between injection points was maintained. The highest total overall RZL-012 dose tested to date was 180 mg, which is 75% of the NOAEL. No serious adverse events were associated with this dose per injection site, with the distance maintained between injection sites or with the maximal overall dose.

In the current trial, a maximal dose of up to 240 mg (33% higher than the maximal dose tested in humans) will be injected per subject. This will allow injection of the desired number of lipomas per patient (4-8 lipomas).

The dosage of RZL-012 per each lipoma was set according to its size (diameter), as determined by ultrasound, and is higher than dosage per lipoma in the previous study. This alteration was made to enhance efficacy of RZL-012. Injections will be comprised of 5 mg each, and will be spread randomly on lipoma surface with a distance between injections of at least 1 cm. A distance of 1 cm will allow a good distribution RZL-012 into lipoma fat.

2.5. DOSING

2.5.1. Dosing Regimen

All subjects will receive a single treatment of RZL-012 or placebo in multiple injection sites according to lipomas size, as shown in Table 2 below.

All subjects assigned to the RZL-012 treatment group will be dosed at a maximal dose of 240 mg RZL-012. Dosing will be calculated according to lipoma size (diameter) as determined by ultrasound in a dose of 5mg per in a volume of 0.1ml. Placebo treated subjects will be dosed with the same vehicle volume as calculated for the RZL-012 group.

Table 2: Study Design

Number of Subjects –	19/19						
Active/Placebo							
Dose of RZL-012(mg)/vehicle (mL) per single injection	5mg/0.1mL						
Lipoma/Nodule size – diameter (cm)	1-1.9	2-3.9	4-5.9	6-7.9	8-10		
Total Dose of RZL-012 in the RZL group (mg)	10	20	40	50	60		
Number of Injections	2	4	8	10	12		

Injections will be given perpendicular (90°) to injected skin surface and will be spread randomly, at least 1cm apart.

Dosing of subjects in Open Label Extension Phase:

Dosing will be calculated according to lipoma size (diameter) as determined by ultrasound and will follow the treatment regimen as shown in Table 2.

3. STUDY ENDPOINTS

The primary and secondary endpoints described below relates to the placebo-controlled phase of the study:

3.1. PRIMARY ENDPOINTS

The primary endpoint for this trial is the average percent reduction in lipoma/nodule height on day 84 after injection vs baseline, in the RZL treated group as compared to the placebo treated group. Lipoma height will be assessed by ultrasound.

A total of 38 subjects will be randomized to receive active treatment or placebo (1:1) at 4 clinical sites. Subjects will be dosed according to size/diameter of selected lipomas with a dose of up to 240 mg RZL-012/patient in the RZL-012 group or up to 4.8mL vehicle/patient in the placebo group.

3.2. KEY SECONDARY ENDPOINT:

The key secondary endpoint for this trial is the average percent reduction in lipoma/nodule pain on day 84 after injection vs baseline, in the RZL-treated group as compared to the placebotreated group. Lipoma pain will be assessed by the Comparative Pain Scale.

3.3. OTHER SECONDARY ENDPOINTS

- 1. Safety and tolerability of RZL-012 dosing to DD subjects vs. placebo dosed subjects.
- 2. Percent responding lipomas/nodules (a responding lipoma is defined as having more than 75% height reduction on day 84 after injection vs baseline), in the RZL treated group as compared to the placebo treated group.

3.4. EXPLORATORY END POINTS

Assessment of Improvement in Quality of Life using QOL questionnaire following treatment.

3.5. OPEN LABEL EXTENSION PHASE ENDPOINTS:

3.5.1. Primary end point:

Average percent reduction in lipoma/nodule height on day 84 after injection vs baseline

3.5.2. Secondary end points:

- 1. Reduction in local pain score per lipoma/nodule on Day 84 vs baseline as measured by comparative pain scale.
- 2. Evaluation of RZL-012 injection safety and tolerability
- 3. Improvement in Quality of life QOL questionnaire

4. STUDY POPULATION

4.1. INCLUSION CRITERIA

Subjects meeting all of the following criteria will be eligible for study participation:

- 1. Women and men, 18-70 years old.
- 2. At least 4 painful lipomas of appropriate size to be injected on a background of DD.
- 3. Generally considered healthy according to medical history, physical examination, electrocardiogram (ECG) and laboratory evaluation with an emphasis on metabolic parameters (fasting glucose concentration < 200 mg/dL).

- 4. Subjects must be able to adhere to the visit schedule and protocol requirements and be capable of completing the study.
- 5. Males or females in the age of fertility are willing to refrain from sexual activity or agree to use a double-barrier contraceptive device (e.g., condom and spermicide) for 4 weeks after treatment with RZL-012.
- 6. Subjects must sign an informed consent indicating they are aware of the investigational nature of the study.

4.2. EXCLUSION CRITERIA

Subjects meeting any of the following criteria will be excluded:

- 1. Unable to tolerate subcutaneous injections.
- 2. Pregnant women.
- 3. Subjects with uncontrolled cardiac, hepatic, renal or neurologic/psychiatric disorders, that in the opinion of the investigator places the subject at significant risk.
- 4. Positive blood screen for Hepatitis B surface antigen (HbSAg), Hepatitis C virus (HCV), or Human immunodeficiency virus (HIV).
- 5. Subjects with a clinical history of active primary or secondary immunodeficiency, autoimmune disease or subjects taking immunosuppressive drugs such as corticosteroids.
- 6. Subjects with dysfunctional gallbladder activity, e.g. underwent cholecystectomy or cholecystitis.
- 7. As a result of medical review and physical examination, the PI (or medically qualified nominee) considers the subject unfit for the study.
- 8. Known sensitivity to components of the injection formulation.
- 9. Prior wound, tattoo or infection in the treated area.
- 10. Prior invasive treatment such as surgery or injectable drug at the RZL-012 injected area.
- 11. Subjects treated chronically at least 3 months prior to study entry with systemic steroids or immunosuppressive drugs.
- 12. Subjects treated chronically at least one week prior to study entry with Non-Steroidal Anti-Inflammatory Drugs (NSAIDs).
- 13. Current participation or participation within 3 months prior to the start of this study in a drug or other investigational research study.

4.3. SUBJECT IDENTIFICATION

At each site, a unique code number will be assigned by the investigator to the trial subject rather than the subjects' names, personal identification numbers, and/or addresses to protect the subject's identity. The code numbers will be used in lieu of the subject's name when the investigator reports AEs and/or other trial related data.

4.4. REMOVAL, REPLACEMENT OR EARLY WITHDRAWAL OF STUDY SUBJECTS

Study subjects withdrawing prior to injection (withdrawal between screening and baseline visits) will be replaced. Subjects withdrawing after injection on baseline visit will not be replaced and will be followed up as possible. Subjects experiencing serious side effects will be withdrawn from the study and followed up until the event resolves or becomes stable.

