5.2.3. Study Treatment

5.2.3.1. Treatment with RZL-012 Investigational Drug

RZL-012 or vehicle will be supplied as a single vial for a single treatment session per subject. Up to 48 injections will be dosed to 4-8 lipomas per each subject.

Overall dose, dosing regimen and injection technique is crucial for safety of study participants.

Syringes will be filled with the desired volume for injection of RZL-012 or vehicle. All injections will be administered at 90° to injected skin, using a 1 mL Luer-lock syringe and a 30 G x 1/2" needle.

The hole of the needle should be pointing into the fat layer. An attempt to pull the plunger should be made before injecting to ensure that no blood is coming out. If so, the plunger should be pushed down to inject the medicine. The formulation is viscous and therefore resistance is expected while injecting.

[figure not shown]
The injected volume will be calculated according to lipoma size (Table 3):

Table 3: Injected volume and dosages of RZL-012 / Placebo according to lipoma size

Number of Subjects – Active/Placebo	19/19				
Lipoma/Nodule size – diameter (cm)	1-1.9	2-3.9	4-5.9	6-7.9	8-10
Total Dose of RZL-012 in the RZL group (mg)	10	20	40	50	60
Number of Injections	2	4	8	10	12

Injections will be given perpendicular (90°) to injected skin surface towards the center of the nodule and the distance between injections in a nodule will be at least 1 cm (Figure 1). The dosing will be done in gradual injections of each 0.1mL into the tissue.

Figure 1: RZL-012/ Placebo Injection Sites in DD Subjects

Each RZL-012 kit contains 1 vial (250 mg/5 mL) enabling injection of the maximal dose per subject, 240mg. RZL-012 or vehicle will be injected on study Day 0 visit (baseline).

After completing injections of lipomas, an ice/cold pack will be applied onto the injection sites for immediate pain relief and will be held by the subject for at least 2 minutes. Following completion of injection procedures, subjects will remain in the clinic for an additional 2 hours ± 30 min for medical supervision and in order to follow adverse events after injection. During the stay in the clinic there are no restrictions in terms of activity or diet.

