5.2.7. Termination Visit

Once study is discontinued, all reasonable measures should be taken to perform a termination visit. Termination visit should include all procedures necessary to complete subjects' records: AE reporting, evaluation of response and updating of subject contact information. An effort should be made to perform all activities conducted on visit Day 84 for subjects who participates in the double-blind randomized placebo controlled study.

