7.3. PREMATURE DISCONTINUATION FROM STUDY

Study may be prematurely discontinued in any of the following cases:

- Subject's request.
- Any life-threatening AE.
- Systemic hypersensitivity reaction.
- Any serious or severe ADR (defined in Section 9.3) clinically evaluated by the PI and/or Sponsor as warranting subject discontinuation.
- Non-compliance: Subject's non-compliance with study procedures, evaluated by PI and/or Sponsor as warranting subject discontinuation.
- Other reasons regarded by PI as warranting subject's discontinuation.
- Premature study termination as described in Section 7.4.

Subjects who discontinue the study prematurely will be queried whether an AE contributed to their decision.

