9.1.2. Definition of Serious Adverse Event

A SAE is defined as any AE occurring at any dose that results in any of the following outcomes:

- death
- a life-threatening AE, as defined below
- subject hospitalization or prolongation of existing hospitalization
- a persistent or significant disability/incapacity
- a congenital anomaly/birth defect
- important medical event, as defined below

A life-threatening AE is any AE that places the subject, in the view of the investigator, at immediate risk of death from the reaction as it occurred (i.e., it does not include a reaction that, had it occurred in a more severe form, might have caused death).

An important medical event is an AE that may not result in death, be life-threatening, or require hospitalization but may be considered a serious AE when, based upon appropriate medical judgment, may jeopardize the subject and may require medical or surgical intervention to prevent one of the outcomes listed above. It can also include AEs otherwise judged to be serious by either the investigator or the Sponsor.

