9.1.3. Definition of Adverse Drug Reaction

AEs associated with the use of investigational product (i.e., probably or possibly related to treatment as defined in Section 9.3) are also termed ADRs.

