11. DATA COLLECTION, STUDY MONITORING, AND DATA DISCLOSURE

11.1. DATA COLLECTION AND REPORTING

Each study subject will be assigned an individual CRF that will contain all of the relevant study information. The investigator shall ensure that all data is completely and accurately recorded on the CRFs throughout trial duration.

Data reported on the CRF that are derived from source documents should be consistent with the source documents or the discrepancies should be explained.

All fields and blanks in the CRFs will be completed. The following abbreviations are to be used when values or answers are not available: NA = Not applicable, ND = Not done, UNK = Unknown, CONT = Continued.

Any change or correction to a CRF should be dated, initialed, and explained (if necessary) and should not obscure the original entry (i.e., an audit trail should be maintained). If an entry on a CRF form is changed, the correction will be made as follows: A single line will be drawn through the incorrect entry, the date and initials of the reporting individual will be added beside the entered change and/or correction, and an explanation will be added when applicable.

When a subject withdraws from the study, regardless of cause, all final study evaluations should be attempted.

If a subject is lost to follow-up, (i.e., fails to return for scheduled visits) every reasonable effort must be made to contact the subject in order to determine why the subject failed to return. All actions taken in this regard will be documented and dated in the CRF.

Once completed, a copy of each completed CRF will be signed and dated by the investigator or a designated representative and submitted to the Sponsor.

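### Section 4.4 requires study withdrawal for undefined serious side effects; after the single Day 0 session this stops no blinded dosing but can lose Day 84 values

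*Combined protocol and SAP*

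**What the plan says.** Section 4.4 sets a mandatory rule: "Subjects experiencing serious side effects will be withdrawn from the study and followed up until the event resolves or becomes stable". The sentence before it says that subjects who withdraw after injection are not replaced and are followed to the extent feasible.

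Section 7.3 treats discontinuation as something that may happen. For drug reactions its trigger is: "Any serious or severe ADR (defined in Section 9.3) clinically evaluated by the PI and/or Sponsor as warranting subject discontinuation". Life-threatening events and systemic hypersensitivity appear in the same list without that judgement clause, but still under the permissive lead-in.

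The term in 4.4 is not one that the protocol defines. Section 9.1.2 defines the SAE ("A SAE is defined as any AE occurring at any dose that results in any of the following outcomes") and 9.1.3 defines ADRs as "AEs associated with the use of investigational product". Section 4.4 points to neither.

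On treatment, 5.2.3.1 says "RZL-012 or vehicle will be supplied as a single vial for a single treatment session per subject" and "The dosing will be done in gradual injections of each 0.1mL into the tissue". The primary and key secondary endpoints (3.1, 3.2) are both read at Day 84, with ultrasound and pain also scheduled at Days 28 and 56. Section 10.5 rules out imputation.

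Two further provisions apply when a subject leaves. Section 5.2.7, on the termination visit: "An effort should be made to perform all activities conducted on visit Day 84". Section 11.1: "When a subject withdraws from the study, regardless of cause, all final study evaluations should be attempted".

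**The concern.** Withdrawing a subject from a study is usually a way to stop exposure. Here, once the Day 0 session is complete, no blinded-phase exposure is left to stop. What withdrawal can end is the remaining schedule of ultrasound and pain assessments, including the Day 84 visit that carries both main efficacy endpoints.

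The trigger is a reaction after treatment, so any value lost this way is missing for a reason tied to how the injection was tolerated. That could differ between arms. The per-patient Day 84 comparison would then drop a randomised, dosed subject.

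The wording also lets sites act differently on the same event. If the phrase in 4.4 means a serious ADR, 4.4 requires withdrawal where 7.3 asks for judgement. If it means any SAE, it also reaches an unrelated hospitalisation.

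**Working it through.** **Step 1: the two rules side by side.**

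| | Section 4.4 | Section 7.3 |
|---|---|---|
| Trigger | serious side effects (undefined) | serious or severe ADR |
| Force | mandatory | permissive, on investigator or sponsor judgement |
| Follow-up | of the event, to resolution or stability | not stated |

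The two conflict if the 4.4 term means a serious ADR.

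**Step 2: what withdrawal can stop.** Dosing proceeds in 0.1 mL steps, so stopping mid-session can limit exposure. After the session it stops nothing in the blinded phase. It could still matter for a placebo subject who would later be offered RZL-012 in the extension.

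**Step 3: what secures a Day 84 value after withdrawal.** Section 4.4 offers follow-up as far as feasible; 5.2.7 and 11.1 ask for an attempt at final evaluations. A termination visit takes place when the subject leaves, which may be well before Day 84, and no rule says that its values count as Day 84. The value can therefore be missing, though it need not be.

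**Step 4: the plan's own sample size.** Inputs from Section 10.3: difference 48, SD 50, two-sided alpha 0.05, two-group t-test, 80% power. The effect size is 48/50 = 0.96. The noncentral t calculation gives n = 18.05, rounded up to 19 per group, so the stated figure reproduces. Power at 19 per group is 82.1%. For the key secondary endpoint (51/50 = 1.02), power at 19 per group is 86.4%.

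**Step 5: power if active subjects are lost.** The documents give no serious-event or dropout rate. I assume that 1 or 2 of 19 active subjects are lost (1/19 = 5%, 2/19 = 11%) and none on placebo. Noncentrality = difference / (SD × √(1/n1 + 1/n2)), df = n1 + n2 − 2.

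| Active/placebo | Noncentrality (primary) | df | Primary power | Key secondary power |
|---|---|---|---|---|
| 19/19 | 2.96 | 36 | 82.1% | 86.4% |
| 18/19 | 2.92 | 35 | 81.0% | 85.4% |
| 17/19 | 2.88 | 34 | 79.8% | 84.3% |

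**Step 6: shift in the observed active mean.** Suppose the mean reduction over all 19 active subjects is 55% and each of k missing subjects has reduction x, with x assumed to lie between 0% and 100%. Shift = (19 × 55 − k·x)/(19 − k) − 55.

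- k = 1: x = 0 gives 1045/18 − 55 = +3.1; x = 100 gives 945/18 − 55 = −2.5.
- k = 2: x = 0 gives 1045/17 − 55 = +6.5; x = 100 gives 845/17 − 55 = −5.3.

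The planned difference is 48 points and its planned standard error is 50 × √(2/19) = 16.2. The largest one-subject shift is 3.1/16.2 = 0.19 standard errors.

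**Step 7: a scale for the number lost.** Section 1.2 counts 54 exposed subjects at doses up to 180 mg. If none had a related serious event (an assumption), the one-sided 95% upper limit is 1 − 0.05^(1/54) = 5.4%, and 19 × 0.054 = 1.03 subjects. This is an upper limit at lower doses, not an expected count.

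**The case against.** The best defence is that the protocol does not abandon these subjects. Section 4.4 itself provides follow-up as far as feasible after post-injection withdrawal, and 5.2.7 and 11.1 ask for response and final evaluations. A site acting on the spirit of these sections might well bring the subject back at Day 84. That stands as mitigation, and it rules out a stronger reading that a reader might take from 4.4 alone: that withdrawal ends all assessment and the Day 84 value is certainly lost. The documents support only that it can be lost, because no provision fixes an assessment at that day.

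The undefined term is also a modest fault. Many sites would read it as a serious ADR, and the conflict with 7.3 depends on that reading.

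The consequence rests on assumed losses. Section 2.4 reports no serious adverse events associated with the doses tested, up to 180 mg, although 240 mg is untested. The mean shifts take the lost subjects to the ends of the assumed range. A reader might infer that the rule biases the result in favour of RZL-012, or leaves the trial underpowered. The documents support neither: the shift can go either way, and the power loss is one or two points.

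Finally, the planned per-lipoma MMRM might be thought to solve the problem. Section 10.4.1 mentions efficacy analyses at Days 28, 56 and 84, but Section 10.2 does not say that the model uses those visits. Which visits it uses is a separate specification question, and settling it would not restore a subject to the per-patient Day 84 test.

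**Conclusion.** The point holds as a minor one. Followed as written, 4.4 can remove a dosed subject's Day 84 height and pain values because of a reaction to treatment, with no gain in blinded-phase safety once the session is over, and it sits awkwardly with 7.3. The existing provisions soften this without closing the gap.

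The size is small on any reasonable assumption. Losing one active subject keeps primary power above 80%, losing two leaves it at about 80%, and the key secondary endpoint stays above 84%. These figures assume 1 or 2 losses, all on active, and the plan's own effect and SD. The direction of any bias is unknown. The case for acting is that the better rule costs almost nothing.

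**What to change.** Replace the mandatory sentence in Section 4.4 with:

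> A serious adverse event stops any remaining Day 0 injections and may bar the open-label injection at the investigator's discretion; the event is followed until it resolves or becomes stable, and dosed subjects otherwise remain in the study and attend the scheduled Day 28, 56 and 84 assessments unless they withdraw consent or the investigator judges attendance unsafe.

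This uses a defined term and covers the one setting in which later dosing is possible. It also keeps follow-up of the event itself. That clause must not be lost, because Section 9.4.1 follows only ADRs, and for at most 6 months.

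Align Section 7.3 so that discontinuation for an adverse event means stopping treatment, not ending follow-up.

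The cost is minor wording in two sections and continued contact with subjects who had a serious event, at visits already scheduled. No subjects or procedures are added.
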